4.0 Study Description

To address the aims outlined above, we propose the Mode Of Ventilation During Critical IllnEss (MODE) Pilot Trial. This trial will be a prospective, single-center, unblinded, cluster-randomized, multiple-crossover trial conducted in the medical ICU at Vanderbilt University Medical Center. During the 9 months of enrollment in the MODE trial, the entire medical ICU will be assigned to a single ventilator mode with the assigned mode alternating between volume control, pressure control, and adaptive pressure control modes every month in a randomly generated sequence. All patients who receive invasive mechanical ventilation and meet inclusion criteria without meeting exclusion criteria will be enrolled at the initiation of mechanical ventilation. The trial will control only the ventilator mode

during controlled mechanical ventilation. All other aspects of clinical care for patients will remain at the discretion of treating clinicians.

4.1 Rationale for Cluster-Level Allocation:

Group assignment in the MODE trial occurs at the level of the ICU (cluster) for multiple reasons. In routine clinical care in the study ICU, 2 to 4 respiratory therapists set the ventilator mode and adjust settings to maintain gas exchange and patient comfort for all mechanically ventilated adults, with input from nurses and physicians. The management of mechanical ventilation (selection of fraction of inspired oxygen, titration of positive end-expiratory pressure, screening for and performance of spontaneous breathing trials) is governed by unit-wide protocols implemented by the 2 to 4 respiratory therapists for all patients in the unit. Assigning the entire unit to a single ventilator mode both emulates the way mechanical ventilation is managed during clinical care and limits contamination that might result from a respiratory therapist managing multiple patients assigned to different modes of mechanical ventilation.

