- **The intervention is delivered by unit-level protocols.** Mechanical ventilator settings and titrations are performed by respiratory therapists using unit-level protocols. In this cluster-randomized trial, the entire unit will be assigned to the same mode of mechanical ventilation for each 1-month block. Obtaining informed consent from every eligible patient in the ICU prior to emergency tracheal intubation and initiation of mechanical ventilation would be impracticable.

Because the study involves minimal risk, the study would not adversely affect the welfare or privacy rights of the participant, and obtaining informed consent would be impracticable, we will request a waiver of informed consent. Numerous previous randomized trials comparing two standards of care for interventions such as emergency intubation and methods of respiratory support during critical illness have been completed with waiver of informed consent.^{39–47}

6.5 Randomization:

During each one-month block of the study, the ICU will be assigned to either volume control, pressure control, or adaptive pressure control. The order of the study group assignments will be generated by computerized randomization using permuted blocks of 3 to minimize the impact of seasonal variation. The last 3 days of each block will be a washout period during which the ICU will continue to use the assigned mode, but new patients will not be included in the primary analysis. The 3-day washout period will limit the number of patients who experience a ‘crossover’ from one assigned mode to another while receiving a mandatory mode of mechanical ventilation.

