10.0 Statistical Considerations

Sample size justification.

The purpose of this trial is to assess feasibility of a cluster-randomized, cluster-crossover design. To assess whether compliance can be maintained after cross-over events, we will need to observe two cross-over events to each mode while maintaining an equal number of treatment blocks for each mode. Doing so will require a total of 9 months. Based on the experience of a prior trial in the same ICU,⁷⁰ we anticipate an average of 75 patients on mechanical ventilation will be enrolled per month. In 9 months, we expect to enroll 675 patients, of whom 69 will be enrolled during washout periods and excluded from the primary analysis. The resulting 606 patients will be included in the primary analysis.

While the sample size was determined to demonstrate feasibility of the cluster-crossover design, we anticipate this pilot will be the largest randomized trial of ventilator modes to date, and as such, we plan to compare ventilator free days to day 28 (primary outcome) between groups. In a prior cluster-randomized cluster-crossover trial in the same ICU,⁷⁰ mechanically ventilated patients experienced a median of 22 VFDs [IQR 0-25 VFDs] and an intra-cluster intra-period correlation of 0.01. With 606 (202 in each group) patients in the primary analysis, a standard deviation in the primary outcome of VFDs of 11 days, and a two-sided alpha of 0.05, the MODE trial will have 80 percent statistical power to detect an absolute difference between groups in the sole primary clinical endpoint of Ventilator Free Days of 3 days.

Primary Analysis of the Primary Clinical Outcome

The sole pre-specified primary outcome of ventilator free days will be compared between the three trial groups in an intention-to-treat fashion among all patients enrolled in the trial except those admitted during one of the 3-day washout periods. To estimate the conditional effect of a group assignment on an individual patient given the values of the covariates for that patient, we will use a proportional odds model with independent covariates of group assignment (volume control, pressure control, or adaptive

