Each of the exploratory outcomes will be compared between groups in an intention-to-treat fashion in the primary analysis population. Continuous outcomes will be compared between groups in a similar manner as the primary clinical outcome. A logistic model will be used for binary outcomes, a multinomial model for categorical outcomes, and a proportional odds model for ordinal and continuous outcomes.

Corrections for multiple testing

We have pre-specified a single primary clinical outcome, which will have a test of statistical significance for difference between groups. Consistent with recommendations of the Food and Drug Administration and the European Medicines Association, the clinical outcome will be tested using a two-sided p-value with a significance level of 0.05. For all other analyses, emphasis will be placed on the estimate of effect size with 95% confidence intervals, as recommended by the International Committee of Medical Journal Editors, and no corrections for multiple comparisons will be performed.

Handling of missing data

The primary outcome is not anticipated to be missing for any patients. Missing data will not be imputed for the primary outcome or any secondary or exploratory outcomes. In adjusted analyses, missing data for covariates will be imputed using multiple imputations.

Interim Analysis

In addition to ongoing monitoring of safety throughout the trial, we will plan for the DSMB to conduct a single interim analysis for safety after the ICU has been assigned to each of the three study modes, that is, after enrollment of patients for 3 months. At the interim analysis, the DSMB will evaluate the incidence of the following outcomes across the study groups (volume control, pressure control, or adaptive pressure control):

- Pneumomediastinum or pneumothorax during the course of mechanical ventilation,
- Episodes of hypoxemia while receiving invasive mechanical ventilation: SpO₂ < 85% for more than 5 minutes,
- In-hospital mortality to study day 28.

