The stopping boundary for safety will be met if the P value for the difference between groups is 0.016 or less, which is an a priori threshold determined by adjusting the p-value threshold of 0.05 for multiple comparisons by dividing 0.05 by the 3 outcomes. The DSMB will consider whether it is necessary to stop the trial or whether randomization to any one study group should be stopped, while the other two groups continue enrolling patients. Given the design of the study is to demonstrate feasibility and pilot trial procedures rather than demonstrating efficacy, there will be no stopping boundary for efficacy or futility.

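### At the 3-month interim each mode has had one calendar month in one ICU, so the P ≤ 0.016 safety boundary cannot separate mode from month and lacks its intended error rate

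*Combined protocol and SAP*

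**What the plan says.** Section 4.0 describes the design: "This trial will be a prospective, single-center, unblinded, cluster-randomized, multiple-crossover trial". Section 6.5 adds: "During each one-month block of the study, the ICU will be assigned to either volume control, pressure control, or adaptive pressure control". The order comes from "computerized randomization using permuted blocks of 3 to minimize the impact of seasonal variation", so each mode appears once in months 1 to 3.

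Under Interim Analysis in section 10.0, the DSMB makes a single comparison "after the ICU has been assigned to each of the three study modes, that is, after enrollment of patients for 3 months". It covers three outcomes: pneumomediastinum or pneumothorax, episodes of hypoxemia, and in-hospital mortality to study day 28. The rule is: "The stopping boundary for safety will be met if the P value for the difference between groups is 0.016 or less". The threshold is obtained by "adjusting the p-value threshold of 0.05 for multiple comparisons by dividing 0.05 by the 3 outcomes". If it is met, the DSMB considers stopping the trial, or whether "randomization to any one study group should be stopped, while the other two groups continue enrolling patients".

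The interim text names no test, time term, allowance for within-month correlation, analysis population (with or without washout enrolments) or data-cut date.

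**The concern.** Dividing 0.05 by 3 limits false alarms across three outcomes. It does nothing about differences between months in case mix, season, staffing or coding. Permuted blocks balance such differences through repetition, and after one permuted block there has been none. A patient-level comparison therefore reads any month effect as a mode effect.

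Elsewhere the plan accepts that time matters. The sample-size paragraph gives an intra-cluster intra-period correlation of 0.01, and the primary model carries a spline in calendar time. The interim rule has neither.

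The mortality outcome raises a second question. It runs to day 28, but patients enrolled late in month 3 have not reached day 28 when that month ends. The first two modes would have complete follow-up and the third would not.

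At stake is the only formal between-group safety comparison in nine months, and a DSMB discussion about dropping a mode because of one unusual month. The reverse error is also possible: a favourable month, or incomplete follow-up, could make a mode look safer than it is.

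**Working it through.** **The plan's own figure.** 0.05/3 = 0.01667, cut to 0.016, which is slightly conservative and harmless. With independent patients and independent outcomes, the chance of any crossing is 1 − (1 − 0.016)³ = 4.7%, as intended.

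**Inputs.**
- Patients per month: "we anticipate an average of 75 patients on mechanical ventilation will be enrolled per month", or 606/9 = 67.3 without washout enrolments.
- Correlation: 0.01, given for ventilator-free days only; 0.002 and 0.005 are assumed alternatives.
- Mortality: 25–35% (section 2.0).
- Test: the plan names none, so a three-group chi-square on independent patients (2 df) is assumed.

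**Degrees of freedom.** Three months and three modes leave 3 − 3 = 0 df for month-to-month variation. The interim data cannot estimate that variation, so the DSMB could not correct for it from what it sees.

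**False crossing.** For 2 df, P(χ² > x) = exp(−x/2), so the threshold is x = −2 ln 0.016 = 8.27. If outcomes within a month share correlation ρ, the statistic is inflated by about DE = 1 + (m − 1)ρ. The false-crossing rate becomes exp(−8.27/(2·DE)) = 0.016^(1/DE).

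| ρ | DE (m = 67.3) | False crossing per outcome |
|---|---|---|
| 0 | 1.00 | 1.6% |
| 0.002 | 1.13 | 2.6% |
| 0.005 | 1.33 | 4.5% |
| 0.01 | 1 + 66.3 × 0.01 = 1.66 | 8.3% |

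With washout patients included (m = 75) and ρ = 0.01, DE = 1.74 and the rate is 9.3%.

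Beta-binomial simulation (200,000 runs, 67 per mode, ρ = 0.01) gives 8.3–8.5% for event rates of 25–35%. For a rare outcome the rate is lower: 3.4% at an assumed 2% event rate, where the same test crosses in only 0.4% at ρ = 0.

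**Would the primary model's time term help?** No. Adding a linear or spline time term to three consecutive one-month blocks inflates the variance of the first-versus-third-month contrast about 11- to 12-fold, and that of adjacent months 3.4- to 4.9-fold. A step-like month effect would still remain.

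**Incomplete deaths, if data were cut on day 30 of month 3.** Assume uniform enrolment over 30 days and exponential times to death with mean τ, truncated at 28 days. The share of third-month deaths seen is

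{[28 − τ(1 − e^(−28/τ))]/(1 − e^(−28/τ)) + 2}/30.

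- τ = 5: (23.10 + 2)/30 = 84%.
- τ = 12: (19.01 + 2)/30 = 70%.

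A true 30% mortality would then show as 25% or 21% for the third mode. Leaving out enrolments in the last 3 days averages the same curve over follow-up of 3 to 30 days. That gives (22.36 + 2)/27 = 90% and (18.62 + 2)/27 = 76%. With the cut 28 days after the last included enrolment the share is 100%.

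**The case against.** The strongest reply is that the boundary is advisory. Crossing it makes the DSMB consider action, and section 13.0 gives the board power to recommend and members with biostatistics and trial expertise. Other safeguards run throughout: daily adverse-event evaluation (section 9.2), 7-day reporting of serious, unexpected, related events (section 9.3), and clinicians' freedom to change mode (section 7.1). In safety monitoring, some extra false alarms referred to a deliberating board may be acceptable. All of this stands and limits the harm. It does not make the P value informative about mode.

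Four stronger readings are tempting, and the documents do not support them.

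- A reader might infer that the boundary simply has an 8% false-alarm rate. The 0.01 is given only for ventilator-free days. The calculation also treats all of it as month-to-month variation and assumes an unadjusted test. Only a conditional range is defensible.
- A reader might combine the three outcomes into one overall false-alarm rate. That needs independence among hypoxemia, pneumothorax and death in the same patients, and event rates for the first two that the documents do not give.
- A reader might infer that the third mode's deaths will be under-counted. No section fixes the data cut, and waiting for day-28 follow-up is consistent with the text.
- A reader might conclude that the formal test should move to six months with block-level variance. Six months and three modes leave 3 residual df (critical F at 0.016 is 22.1). In simulation at ρ = 0.01 with 67 patients per month, that test crosses in 9% of trials when one mode raises mortality from 30% to 45%, and in 15% when it raises it to 50%. The planned 3-month test crosses in 37% and 56%, partly through its inflated error. The later test would be too insensitive to protect patients.

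**Conclusion.** The point holds. The confounding of mode with month at the interim follows from the design and timing alone and needs no assumption. As a result the 0.016 threshold does not deliver the error control that its derivation implies.

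The size is conditional. For a common outcome the false-crossing rate is about 2.6% to 8.3% over correlations of 0.002 to 0.01, against 1.6% nominal. This assumes about 67 patients per mode, a patient-level test, and correlation that acts wholly between months; stable features of the single ICU would cancel. It is lower for pneumothorax if that is rare.

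The mortality point is an unstated data cut, not a demonstrated bias. If there were no lag, about 70–84% of third-month deaths would be seen under the assumed mean times to death of 12 to 5 days with enrolment over the full month. A crossing leads to deliberation and does not stop the trial by itself.

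**What to change.** Keep the 3-month DSMB review and change four things in the protocol and DSMB charter.

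1. Report incidence by mode with confidence intervals widened by the design effect: about 1.66 at ρ = 0.01, which multiplies the half-width by √1.66 = 1.29. Show a range of ρ, because the interim data cannot estimate it. For 30% of 67 patients, the half-width goes from 1.96 × √(0.3 × 0.7/67) = 11 points to 11 × 1.29 = 14 points.
2. State that mode and month cannot yet be separated, and that P ≤ 0.016 is a trigger for closer review and not evidence of a mode effect.
3. Compare mortality only over follow-up that all included patients have completed, for example by cutting the data 28 days after the last included enrolment.
4. Name the interim test and say whether washout enrolments count.

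A descriptive DSMB report at six months, with two months per mode, is optional.

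The cost is wording, wider intervals, and mortality data that arrive up to 28 days later or cover a shorter window. No safety review is lost.

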11.0 Privacy / Confidentiality Issues

At no time during this study, its analysis, or its publication, will patient identities be revealed in any manner. The minimum necessary data containing patient or provider identities will be collected. Data collected from the medical record and the Mode Modification Sheets will be entered into the secure online database REDCap. Only key study personnel will have access to the REDCap database. Hard copies of the treating clinician Mode Modification Sheet will be stored in a locked room until after the completion of enrollment and data cleaning.

All data will be maintained in the secure online database REDCap until the time of study publication. At the time of publication, a de-identified version of the database will be generated.

12.0 Follow-up and Record Retention

Patients will be followed after enrollment for 28 days or until hospital discharge, whichever occurs first. Data collected from the medical record will be entered into the secure online database REDCap. Hard copies of the treating clinician Mode Modification Sheet will be used for manual data entry into the REDCap database and stored in a locked room until after the completion of enrollment and data cleaning. All data will be maintained in the secure online database REDCap until the time of study publication. Once data are verified and the database is locked, all hard copies of Mode Modification Sheets will be destroyed. At the time of publication, a de-identified version of the database will be generated.

13.0 Data Safety and Monitoring Board (DSMB)

The principal role of the DSMB is to assure the safety of patients in the trial. They will regularly monitor data from this trial, review and assess the performance of its operations, and make recommendations to the steering committee and sponsor with respect to:

- Participant safety and risk/benefit ratio of study procedures and interventions
- Protocol amendments (with specific attention to study population, intervention, and study procedures)
- Adherence to the protocol requirements
- Completeness, quality, and planned analysis of data
- Ancillary study burden on participants and main study
- Possible early termination of the trial because of new external information, safety concerns, or inadequate performance.

The DSMB will consist of members with expertise in critical care medicine, pulmonary medicine, biostatistics, and clinical trials. Appointment of all members is contingent upon the absence of any conflicts of interest. All the members of the DSMB are voting members. The Principal Investigator and unblinded study biostatistician will be responsible for the preparation of all DSMB and adverse event reports. The DSMB will develop a charter and review the protocol and patient notification forms during its first meeting. Subsequent DSMB meetings will be scheduled in accordance with the DSMB Charter with the assistance of the Principal Investigator. The DSMB will have the ability to recommend that the trial end, be modified, or continued unchanged.

 - For **VC and PRVC:** High Peak Pressure alarm at 40 cm H₂O
 - For **PC:** Low Minute Ventilation alarm at 2 L/min less than the current Minute Ventilation
5. Adjust Vt and RR to achieve pH and plateau pressure goals below.

Lung Protective Ventilation Goals – $V_t \leq 6$ mL/kg PBW, Pplat < 30 cmH₂O

**For Pressure Control, where Vt cannot be directly adjusted, adjust PC over PEEP in increments of 2 cmH₂O and monitor resulting Vt to achieve the changes outlined below.*

If $V_t > 6$ mL/kg PBW:

Reduce Vt by 1 mL/kg at intervals ≤ 2 hours until $V_t = 6$ mL/kg PBW.

If Pplat > 30 (or PIP > 35):

Decrease Vt by 1 mL/kg steps to a minimum of 4mL/kg PBW.

If Pplat < 25 and $V_t < 6$ mL/kg:

Increase Vt by 1 mL/kg until either Pplat > 25 or $V_t = 6$ mL/kg PBW.

If Pplat < 30 and breath stacking occurs:

May increase Vt in 1 mL/kg increments to maximum of 8 mL/kg PBW.

Ventilation Goals - pH: 7.30-7.45

If pH 7.15-7.30:

Increase RR until pH > 7.30 or PaCO₂ < 25 (Max RR = 35).

If RR = 35 and PaCO₂ < 25:

May give NaHCO₃, to be managed by primary team.

If pH < 7.15:

Increase RR to 35.

If pH remains < 7.15 and NaHCO₃ considered or infused:

Vt may be increased until pH >7.15 or Vt = 8 mL/kg PBW (Pplat target may be exceeded).

If pH >7.45:

Decrease RR rate.

Oxygenation goals - SpO₂: 88-95% or PaO₂: 55-80 mmHg.

Use incremental FiO₂/PEEP combinations below to provide minimum FiO₂ and PEEP necessary to achieve PaO₂ or SpO₂ goals.

FiO₂	0.3-0.4	0.4	0.5	0.5	0.6	0.7	0.7	0.7	0.8	0.9	0.9	0.9	1
PEEP	5	8	8	10	10	10	12	14	14	14	16	18	18-25

Other Settings

I:E ratio goal: 1:1.0 – 1-3.0. Adjust Ti to achieve goal.

If FiO₂ = 1.0 and PEEP = 24 cmH₂O, may adjust I:E to 1:1.

Avoid inverse-ratio ventilation.

Trigger: 1.6 L/min by default, can be increased or reduced to improve synchrony

Tinsp rise (s): 0.15 s by default, can be increased or decreased to improve ventilation

Monitoring and Documentation:

Measure & record Pplat with inspiratory pause of at least 0.5 s, SpO₂, Total RR, Vt and pH (if available) at least every 4 hours AND after each change in PEEP, Vt, or PC above PEEP settings.

Once the patient tolerates FiO₂ < 0.5 and PEEP < 8 cmH₂O, advance to Part II: Spontaneous Breathing Trial Readiness Assessment and Ventilator Discontinuation Guidelines.

Appendix 2. Ventilator Guidelines Table

	Volume Control	Pressure Control	Adaptive Pressure Control
Mode option	Volume Control	Pressure Control	Pressure Regulated Volume Control (PRVC)
Tidal Volume target (mL/kg PBW)	6	6	6
Tidal Volume range (mL/kg PBW)	4 - 8	4 - 8	4 - 8
Initial breath settings	Tidal volume to 6 mL/kg PBW	PC over PEEP to 15 cm H20, Insp Time to 0.9 sec	Tidal volume to 6 mL/kg PBW
Achieving target Tidal Volume	Directly adjust tidal volume	Dependent on adjustment of PC over PEEP	Adjust tidal volume directly
Plat Pressure target (cm H20)	≤ 30	≤ 30	≤ 30
Achieving target Plateau Pressure	Dependent on adjustment of tidal volume	Directly adjust PC over PEEP	Dependent on adjustment of tidal volume
Flow	Set directly	Dependent ventilator and patient factors	Dependent ventilator and patient factors
Flow Pattern	Square waveform	Decelerating, dynamic	Decelerating, dynamic
Arterial pH goal	7.3 - 7.45	7.3 - 7.45	7.3 - 7.45
Ventilator rate (breaths/min)	≤ 35	≤ 35	≤ 35
Oxygenation goal by PaO2 (mmHg)	55 - 80	55 - 80	55 - 80
Oxygenation goal by SpO2 (%)	88 - 95	88 - 95	88 - 95
Positive end-expiratory pressure	Set with FiO2-PEEP table	Set with FiO2-PEEP table	Set with FiO2-PEEP table
Inspiratory: Expiratory ratio	1:1 - 1:3	1:1 - 1:3	1:1 - 1:3
Extubation evaluation	MICU SBT Readiness and Extubation Guidelines	MICU SBT Readiness and Extubation Guidelines	MICU SBT Readiness and Extubation Guidelines

